5.6.1 Additional Research

This protocol will include residual sample storage for additional research (AR).

For All US sites:

Additional research is required for all study participants, except where prohibited by IRBs/ethics committees, or academic/institutional requirements. Where one or more of these exceptions occurs, participation in the additional research should be encouraged but will not be a condition of overall study participation.

- If the IRB/ethics committees and site agree to the mandatory additional research retention and/or collection, then the study participant must agree to the mandatory additional research as a requirement for inclusion in the study.
- If optional participation is permitted and approved, then the study participants may opt out of the additional research retention and/or collection.

For non-US Sites:

Additional research is optional for all study participants, except where retention and/or collection is prohibited by local laws or regulations, ethics committees, or institutional requirements.

This collection for additional research is intended to expand the translational R&D capability at Bristol-Myers Squibb, and will support as yet undefined research aims that will advance our understanding of disease and options for treatment. It may also be used to support health

authority requests for analysis, and advancement of pharmacodiagnostic development to better target drugs to the right patients. This may also include genetic/genomic exploration aimed at exploring disease pathways, progression and response to treatment etc.

Sample Collection and Storage

All requests for access to samples or data for additional research will be vetted through a diverse committee of the study sponsor’s senior leaders in Research and Development (or designee) to ensure the research supports appropriate and well-defined scientific research activities.

- Residual samples from biomarker, biopsy and PK sample collections (see Table 5.6.1-1) will also be retained for additional research purposes

Samples kept for future research will be stored at the BMS Biorepository in NJ, USA or an independent, BMS-approved storage vendor.

- The manager of these samples will ensure they are properly used throughout their usable life and will destroy the samples at the end of the scheduled storage period, no longer than fifteen (15) years after the end of the study or the maximum allowed by applicable law.
- Transfers of samples by research sponsor to third parties will be subject to the recipient’s agreement to establish similar storage procedures.

Samples will be stored in a coded fashion, and no researcher will have access to the key. The key is securely held by the Investigator at the clinical site, so there is no direct ability for a researcher to connect a sample to a specific individual.

Further details of sample collection and processing will be provided to the site in the procedure manual.

Table 5.6.1-1: Residual Sample Retention for Additional Research Schedule

Sample Type	Timepoints for which residual samples will be retained
PK	All
Whole Blood	All
Blood RNA	All
PBMCs	All
Serum	All
Saliva	All
Biopsy	All
Biopsy RNA	All

5.7 Outcomes Research Assessments

Questionnaires and investigator/subject assessments will be completed, prior to study drug administration, on either paper forms or an electronic tablet (ePRO) and information gathered on this device will serve as the source document where possible. BMS will provide the appropriate versions of the assessment scales for use by the site. Sites should only use the versions of the scales provided by BMS for this study.

The following additional symptom scales and patient reported outcome measures will be collected:

Completed by Investigator (at baseline/Day 1 and Days 15, 29, 43, 57, 71, 85, and Follow-up Day 127):

- Physician global assessment of disease activity (phyGDA, See [Appendix 6](#))

Completed by subject (at baseline/Day 1 and Days 15, 29, 43, 57, 71, 85, and Follow-up Day 127):

- ESSPRI (see [Appendix 4](#))
- Numeric rating scales (see [Appendices 7, 8, and 9](#)) for ocular, oral and vaginal dryness (females only)
- Subject global assessment of disease activity (SubGDA, See [Appendix 5](#))

Completed by subject (at baseline/Day 1 and Days 29, 57, 85, and Follow-up Day 127)

- PROMIS Fatigue Short Form (see [Appendix 10](#))
- Female Sexual Function Index (FSFI, see [Appendix 11](#))
- Short Form-36 acute (SF-36 acute, see [Appendix 12](#))
- Work Participation Activity Index (WPAI, see [Appendix 13](#))

6 ADVERSE EVENTS

An *Adverse Event (AE)* is defined as any new untoward medical occurrence or worsening of a preexisting medical condition in a clinical investigation subject administered study drug and that does not necessarily have a causal relationship with this treatment. An AE can therefore be any

unfavorable and unintended sign (such as an abnormal laboratory finding), symptom, or disease temporally associated with the use of study drug, whether or not considered related to the study drug. Severity of all adverse events will be graded by using the National Cancer Institute's Common Terminology Criteria for Adverse Events (NCI CTCAE) version 4.03.

The causal relationship to study drug is determined by a physician and should be used to assess all AEs. The causal relationship can be one of the following:

Related: There is a reasonable causal relationship between study drug administration and the AE.

Not related: There is not a reasonable causal relationship between study drug administration and the AE.

The term "reasonable causal relationship" means there is evidence to suggest a causal relationship.

Adverse events can be spontaneously reported or elicited during open-ended questioning, examination, or evaluation of a subject (In order to prevent reporting bias, subjects should not be questioned regarding the specific occurrence of one or more AEs).

Sponsor or designee will be reporting adverse events to regulatory authorities and ethics committees according to local applicable laws including European Directive 2001/20/EC and FDA Code of Federal Regulations 21 CFR Parts 312 and 320.

6.1 Serious Adverse Events

A *Serious Adverse Event (SAE)* is any untoward medical occurrence that at any dose:

- results in death
- is life-threatening (defined as an event in which the subject was at risk of death at the time of the event; it does not refer to an event which hypothetically might have caused death if it were more severe)
- requires inpatient hospitalization or causes prolongation of existing hospitalization (see **NOTE** below)
- results in persistent or significant disability/incapacity
- is a congenital anomaly/birth defect
- is an important medical event (defined as a medical event(s) that may not be immediately life-threatening or result in death or hospitalization but, based upon appropriate medical and scientific judgment, may jeopardize the subject or may require intervention [eg, medical, surgical] to prevent one of the other serious outcomes listed in the definition above.) Examples of such events include, but are not limited to, intensive treatment in an emergency room or at home for allergic bronchospasm; blood dyscrasias or convulsions that do not result in hospitalization.) Potential drug induced liver injury (DILI) is also considered an important medical event. (See [Section 6.6](#) for the definition of potential DILI.)

Suspected transmission of an infectious agent (eg, pathogenic or nonpathogenic) via the study drug is an SAE.

Although pregnancy, overdose, cancer, and potential DILI are not always serious by regulatory definition, these events must be handled as SAEs (see Section 6.1.1 for reporting pregnancies).

Any component of a study endpoint that is considered related to study therapy (eg, death is an endpoint, if death occurred due to anaphylaxis, anaphylaxis must be reported) should be reported as SAE (see Section 6.1.1 for reporting details).

NOTE:

The following hospitalizations are not considered SAEs in BMS clinical studies:

- a visit to the emergency room or other hospital department < 24 hours, that does not result in admission (unless considered an important medical or life-threatening event)
- elective surgery, planned prior to signing consent
- admissions as per protocol for a planned medical/surgical procedure
- routine health assessment requiring admission for baseline/trending of health status (eg, routine colonoscopy)
- medical/surgical admission other than to remedy ill health and planned prior to entry into the study. Appropriate documentation is required in these cases
- admission encountered for another life circumstance that carries no bearing on health status and requires no medical/surgical intervention (eg, lack of housing, economic inadequacy, caregiver respite, family circumstances, administrative reason)
- Admission for administration of anticancer therapy in the absence of any other SAEs (applies to oncology protocols)

6.1.1 Serious Adverse Event Collection and Reporting

Sections 5.6.1 and 5.6.2 in the Investigator Brochures (IBs) represent the Reference Safety Information to determine expectedness of serious adverse events for expedited reporting. Following the subject's written consent to participate in the study, all SAEs, whether related or not related to study drug, must be collected, including those thought to be associated with protocol-specified procedures. All SAEs must be collected that occur during the screening period from the date of subject's written consent until 42 days post discontinuation of dosing.

The investigator must report any SAE that occurs after these time periods and that is believed to be related to study drug or protocol-specified procedure.

An SAE report must be completed for any event where doubt exists regarding its seriousness.

If the investigator believes that an SAE is not related to study drug, but is potentially related to the conditions of the study (such as withdrawal of previous therapy or a complication of a study procedure), the relationship must be specified in the narrative section of the SAE Report Form.

SAEs, whether related or not related to study drug, and pregnancies must be reported to BMS (or designee) within 24 hours of awareness of the event. SAEs must be recorded on the SAE Report Form; pregnancies on a Pregnancy Surveillance Form (electronic or paper forms). The preferred method for SAE data reporting collection is through the eCRF. The paper SAE/pregnancy surveillance forms are only intended as a back-up option when the eCRF system is not functioning. In this case, the paper forms are to be transmitted via email or confirmed facsimile (fax) transmission to:

SAE Email Address: Refer to Contact Information list.

SAE Facsimile Number: Refer to Contact Information list.

For studies capturing SAEs through electronic data capture (EDC), electronic submission is the required method for reporting. In the event the electronic system is unavailable for transmission, paper forms must be used and submitted immediately. When paper forms are used, the original paper forms are to remain on site.

SAE Telephone Contact (required for SAE and pregnancy reporting): Refer to Contact Information list.

If only limited information is initially available, follow-up reports are required. (Note: Follow-up SAE reports must include the same investigator term(s) initially reported.)

If an ongoing SAE changes in its intensity or relationship to study drug or if new information becomes available, the SAE report must be updated and submitted within 24 hours to BMS (or designee) using the same procedure used for transmitting the initial SAE report.

All SAEs must be followed to resolution or stabilization.

BMS will be reporting adverse events to regulatory authorities and ethics committees according to local applicable laws including European Directive 2001/20/EC and FDA Code of Federal Regulations 21 CFR Parts 312 and 320. A SUSAR (Suspected, Unexpected Serious Adverse Reaction) is a subset of SAEs and will be reported to the appropriate regulatory authorities and investigators following local and global guidelines and requirements.

6.2 Nonserious Adverse Events

A *nonserious adverse event* is an AE not classified as serious.

6.2.1 Nonserious Adverse Event Collection and Reporting

The collection of nonserious AE information should begin at initiation of study drug. Nonserious AE information should also be collected from the start of a placebo lead-in period or other observational period intended to establish a baseline status for the subjects.

Nonserious AEs should be followed to resolution or stabilization, or reported as SAEs if they become serious (see [Section 6.1.1](#)). Follow-up is also required for nonserious AEs that cause interruption or discontinuation of study drug and for those present at the end of study treatment as appropriate. All identified nonserious AEs must be recorded and described on the nonserious AE page of the CRF (paper or electronic).

Completion of supplemental CRFs may be requested for AEs and/or laboratory abnormalities that are reported/identified during the course of the study.

6.3 Laboratory Test Result Abnormalities

The following laboratory test result abnormalities should be captured on the nonserious AE CRF page or SAE Report Form (electronic) as appropriate. Paper forms are only intended as a back-up when the electronic system is not functioning:

- Any laboratory test result that is clinically significant or meets the definition of an SAE
- Any laboratory test result abnormality that required the subject to have study drug discontinued or interrupted
- Any laboratory test result abnormality that required the subject to receive specific corrective therapy

It is expected that wherever possible, the clinical rather than laboratory term would be used by the reporting investigator (eg, anemia versus low hemoglobin value).

6.4 Pregnancy

If, following initiation of the study drug, it is subsequently discovered that a study subject is pregnant or may have been pregnant at the time of study exposure, including during at least 5 half-lives after product administration (35 days for lulizumab), the investigator must immediately notify the BMS Medical Monitor (or designee) of this event and complete and forward a Pregnancy Surveillance Form to BMS Designee within 24 hours of awareness of the event and in accordance with SAE reporting procedures described in [Section 6.1.1](#).

In most cases, the study drug will be permanently discontinued in an appropriate manner (eg, dose tapering if necessary for subject safety). Please call the BMS Medical Monitor or designee within 24 hours of awareness of the pregnancy.

Protocol-required procedures for study discontinuation and follow-up must be performed on the subject.

Follow-up information regarding the course of the pregnancy, including perinatal and neonatal outcome and, where applicable, offspring information must be reported on the Pregnancy Surveillance Form.

Any pregnancy that occurs in a female partner of a male study participant should be reported to BMS. Information on this pregnancy will be collected on the Pregnancy Surveillance Form. In order for BMS to collect any pregnancy surveillance information from the female partner, the female partner must sign an informed consent form for disclosure of this information. Information on this pregnancy will be collected on the Pregnancy Surveillance Form.

6.5 Overdose

An overdose is defined as the accidental or intentional administration of any dose of a product that is considered both excessive and medically important. All occurrences of overdose must be reported as an SAE (see Section 6.1.1 for reporting details).

6.6 Potential Drug Induced Liver Injury (DILI)

Wherever possible, timely confirmation of initial liver-related laboratory abnormalities should occur prior to the reporting of a potential DILI event. All occurrences of potential DILIs, meeting the defined criteria, must be reported as SAEs (see [Section 6.1.1](#) for reporting details).

Potential drug induced liver injury is defined as:

1. AT (ALT or AST) elevation > 3 times upper limit of normal (ULN)

AND

2. Total bilirubin > 2 times ULN, without initial findings of cholestasis (elevated serum alkaline phosphatase)

AND

3. No other immediately apparent possible causes of AT elevation and hyperbilirubinemia, including, but not limited to, viral hepatitis, pre-existing chronic or acute liver disease, or the administration of other drug(s) known to be hepatotoxic

6.7 Other Safety Considerations

Any significant worsening noted during interim or final physical examinations, electrocardiogram (ECG), x-ray filming, any other potential safety assessment required or not required by protocol should also be recorded as a nonserious or serious AE, as appropriate, and reported accordingly.

7 DATA MONITORING COMMITTEE AND OTHER EXTERNAL COMMITTEES

A Data Monitoring Committee (DMC) will monitor overall safety data regularly to ensure that the benefits and risks of study participation remain acceptable. Based on the regular reviews of emerging data, the DMC may recommend to the Sponsor alteration and/or termination of the trial or a treatment group, or cessation of further enrollment into a treatment group.

Data summaries and listings will be provided to the DMC to facilitate their safety assessment at the regularly scheduled times as well as on an ad hoc basis if needed. The DMC will review safety data including SAEs and events of special interest, focusing on early signal detection. Further details on the frequency, content, and methods of data reports to the DMC will be outlined in the Charter of that Committee along with the processes and procedures the committee will follow.

8 STATISTICAL CONSIDERATIONS

8.1 Sample Size Determination

The sample size calculation is based on the power to compare change from baseline in ESSDAI at Week 12 between active treatment arms (lulizumab or BMS-986142) and the placebo arm. With a two-sided two-sample t-test at significance level 0.05, data from 25 treated subjects per arm will provide approximately 90% power to detect a placebo-adjusted 3-point decrease from

baseline for each active treatment group, assuming common standard deviations of 3.2.⁶⁶ In addition, the Hochberg's step-up procedure will be used to adjust the multiplicity due to the comparison of two active treatment arms (lulizumab or BMS-986142) to the placebo arm.

The primary efficacy analysis will be conducted on all randomized subjects who received at least one dose of study drug.

An interim analysis will be conducted after at least 30 subjects reach Week 12 (complete 12 weeks of treatment) and complete the specified assessments for ESSDAI. The interim analysis will be conducted in a fully blinded manner such that treatment group assignments of study subjects are not known and are not used in any manner in the analysis. A blinded examination of the variance of the primary endpoint will be performed and compared to the assumption used in planning the study. If this comparison suggests the initial assumption was substantially too low, the total study sample size may be increased by up to 45 additional subjects (ie, to a maximum of 120 subjects in total) to maintain adequate study power.^{67,68,69} Regardless of the outcome from the blinded examination of variability, the study sample size will not be decreased. A maximum study sample size of 120 subjects in total, ie, 40 subjects per arm, can provide each active treatment arm 79% power to detect a placebo-adjusted 3-point decrease from baseline for common standard deviations as large as 4.8, using a two-sided two-sample t-test comparing each active treatment arm to placebo at significant level 0.05.

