The sample size calculation is based on the power to compare change from baseline in ESSDAI at Week 12 between active treatment arms (lulizumab or BMS-986142) and the placebo arm. With a two-sided, two-sample t-test at significance level 0.05, data from 25 treated subjects per arm will provide approximately 90% power to detect a placebo-adjusted 3-point decrease from baseline for each active treatment group, assuming common standard deviations of 3.2. In addition, the Hochberg’s step-up procedure will be used to adjust the multiplicity due to the comparison of two active treatment arms (lulizumab or BMS-986142) to the placebo arm.

The primary efficacy analysis will be conducted on all randomized subjects who received at least one dose of study drug.

An interim analysis will be conducted after at least 30 subjects reach Week 12 (complete 12 weeks of treatment) and complete the specified assessments for ESSDAI. The interim analysis will be conducted in a fully blinded manner such that treatment group assignments of study subjects are not known and are not used in any manner in the analysis. A blinded examination of the variance of the primary endpoint will be performed and compared to the assumption used in planning the study. If this comparison suggests the initial assumption was substantially too low, the total study sample size may be increased by up to 45 additional subjects (ie, to a maximum of 120 subjects in total) to maintain the desired study power. Regardless of the outcome from the blinded examination of variability, the study sample size will not be decreased. A maximum study sample size of 120 subjects in total, ie, 40 subjects per arm, can provide each active treatment arm 79% power to detect a placebo-adjusted 3-point decrease from baseline for common standard deviations as large as 4.8, using a two-sided two-sample t-test comparing each active treatment arm to placebo at significant level 0.05.

Endpoints:

The primary endpoint is to compare the change from baseline in ESSDAI score at Week 12 between active treatment arms (lulizumab or BMS-986142) and the placebo arm.

Secondary Endpoints:

- Change from baseline in ESSPRI score at Week 12
- Proportion of subjects with ≥ 3 points of improvement from baseline in ESSDAI at Week 12
- Proportion of subjects with ≥ 1 point of improvement from baseline in ESSPRI at Week 12

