- Proportion of subjects with both ≥ 3 points improvement in ESSDAI and ≥ 1 point of improvement in ESSPRI from baseline at Week 12
- Change from baseline in:
 - ESSDAI scores at Weeks 4 and Week 8
 - ESSPRI scores at Weeks 4 and Week 8
 - ESSPRI individual component (Dryness, Fatigue, and Pain) scores at Weeks 4, 8, and 12
 - Unstimulated and stimulated salivary flow rate at Weeks 4, 8, and 12
 - Ocular surface staining, Schirmer's test and tear break-up time test at Weeks 4, 8, and 12
- Safety and tolerability of lulizumab or BMS-986142 as measured by adverse events, laboratory parameters, vital signs, physical exams, and ECGs
- Change from baseline in patient and physician assessments of disease activity:
 - Numeric rating scale (NRS) for mouth, eye and vaginal dryness
 - Subject global assessment of disease activity (SubGDA) and physician global assessment of disease activity (phyGDA)
 - Short Form-36 (SF-36)
 - Female Sexual Function Index (FSFI)
 - Work participation and activity impairment questionnaire (WPAI)
 - PROMIS Fatigue Short Form
 - Trough concentrations of BMS-931699 and BMS-986142 at protocol-specified time points

Efficacy Analyses:

Primary efficacy analysis:

The mixed effects model with repeated measures (MMRM) will be used to model the change from baseline in ESSDAI score over time for all treatment arms. Details of the model will be given in the statistical analysis plan. The least square means of the differences of Week 12 change in ESSDAI from baseline between each active treatment and the placebo will be estimated and their corresponding two-sided 95% confidence intervals will be provided. In addition, as part of the secondary objective, similar outputs will be provided for the changes in ESSDAI score at Weeks 4 and 8.

The Hochberg's step-up procedure will be used to adjust the multiplicity due to the comparison of two active treatments (lulizumab or BMS-986142) to the placebo arm in the primary endpoint (ie, change from baseline in ESSDAI at Week 12). The corresponding adjusted p-values for the Hochberg procedure will be provided.

Secondary efficacy analysis:

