8.4.2 Efficacy Analyses

8.4.2.1 Primary Efficacy Analyses

The mixed effects model with repeated measures (MMRM) will be used to model the change from baseline in ESSDAI score over time for all treatment arms. Details of the model will be given in the statistical analysis plan. The least square means of the differences of Week 12 change in ESSDAI from baseline between each active treatment and the placebo will be estimated and their corresponding two-sided 95% confidence intervals will be provided. In addition, as part of the secondary objective, similar outputs will be provided for the changes in ESSDAI score at Weeks 4 and 8.

The Hochberg's step-up procedure will be used to adjust the multiplicity due to the comparison of two active treatments (lulizumab or BMS-986142) to the placebo arm in the primary endpoint (ie, change from baseline in ESSDAI at Week 12). The corresponding adjusted p-values for the Hochberg procedure will be provided.

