7.1.5 Mixed effects Model with Repeated Measures

7.1.5.1 Model Specification

A mixed effect model with repeated measures analysis using ‘direct likelihood’ will be performed. The SAS procedure PROC MIXED will be used.

The dependent variable will be the change from baseline to each Visit t included in the model for efficacy endpoints examining changes from baseline. For analyses of parameters in terms of percent change from baseline at Visit t, values will first be transformed to logarithms and the results will be expressed as geometric mean percent changes from baseline. The dependent variable will be the natural logarithms (Ln) of the post-baseline to baseline ratios. The model estimates will be back transformed to original values using the formulae detailed in [Table 7.1.2-1](#).

The preferred model will include the fixed categorical effects of treatment, visit, randomization stratification factors (i.e. one term for each combination of the stratification factors of hydroxychloroquine and oral corticosteroid use based on IVRS) and treatment-by-visit interaction, as well as the continuous fixed covariates of baseline measurement and baseline measurement-by-visit interaction. For parameters analyzed as percent change from baseline, the natural logarithm of the baseline values will be used in the above model specification. An unstructured matrix for the within-subject error variance-covariance will be used. The denominator degrees of freedom will be calculated according to the Kenward-Roger method.

In case of non-convergence of the preferred model or memory space issues the following back-up models are defined:

- 1) The first backup model is the same as the preferred model but the Kenward-Roger method will be replaced by Satterthwaite approximation.
- 2) The second backup model is the same as the preferred model but without the term for baseline measurement-by-visit interaction.

The second back-up model will only be provided if the first back-up model does not converge or has memory issues.

The model will provide least-squares mean estimates, standard errors and 2-sided 95% confidence intervals for mean change at all time points within and between treatments. Where applicable, for specific visits, the t-statistic corresponding to the Type III sums of squares for the differences in the least squares means will be used to obtain p-values for treatment group comparisons.

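### The 90% and 79% per-arm power figures are for one unadjusted 0.05 test; under the planned Hochberg rule they are 89% and 76% if both drugs work, and 84% and 70% if only one does

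*Protocol*

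**What the plan says.** Protocol 8.1 bases the sample size on a two-sided two-sample t-test at 0.05 of each active arm against placebo. With a common SD of 3.2, its claim for each active group is that "data from 25 treated subjects per arm will provide approximately 90% power to detect a placebo-adjusted 3-point decrease from" the baseline score. It then adds that Hochberg's step-up procedure will deal with the two comparisons. For the maximum of 120 subjects (40 per arm), it says the trial "can provide each active treatment arm 79% power to detect a placebo-adjusted 3-point decrease from baseline for common standard deviations as large as 4.8". The basis it names for that second figure is again a single test per arm: "using a two-sided two-sample t-test comparing each active treatment arm to placebo at significant level 0.05". The Sample Size part of the synopsis gives the same two figures: "data from 25 treated subjects per arm will provide approximately 90% power" and "can provide each active treatment arm 79% power to detect a placebo-adjusted 3-point decrease from baseline".

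The decision rule is in Protocol 8.4.2.1: "The Hochberg's step-up procedure will be used to adjust the multiplicity due to the comparison of two active treatments". The synopsis (primary efficacy analysis) and SAP 7.5.1 say the same, and all three call for Hochberg-adjusted p-values. The analysis model in SAP 7.1.5.1 is an MMRM that has treatment, visit and stratification terms "as well as the continuous fixed covariates of baseline measurement and baseline measurement-by-visit interaction".

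Neither Protocol 8.1 nor the synopsis gives power under Hochberg.

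**The concern.** The 90% and 79% are attached to each active arm, so a reader will take them as the chance that an arm succeeds in the primary analysis. They are the chance that its unadjusted p-value falls at or below 0.05. Under Hochberg with two comparisons, an arm whose p-value lies between 0.025 and 0.05 succeeds only if the other arm is also at or below 0.05. Some of the results counted in the stated power would therefore fail.

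The two drugs have different mechanisms (a CD28 antagonist and a BTK inhibitor), so a trial in which only one works is a realistic outcome, and there the loss is largest.

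The 79% matters most. It is the only power figure in these two sections for the 120-subject maximum. SAP 7.11 ties any increase after the blinded interim look to keeping adequate power and leaves the decision to the sponsor's senior management, who should see power under the rule that will be applied.

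**Working it through.** **Inputs.** Effect 3 points; SD 3.2 with 25 per arm; SD 4.8 with 40 per arm; two-sided 0.05 (all Protocol 8.1). Equal allocation (synopsis, Number of Subjects). Hochberg over two comparisons with a shared placebo arm (Protocol 8.4.2.1, SAP 7.5.1).

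**Step 1: reproduce the stated figures.** The t-statistic has 2n − 2 degrees of freedom and noncentrality 3 / (SD × √(2/n)).

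- n = 25, SD 3.2: 3 / (3.2 × 0.2828) = 3.315 on 48 df. The critical value at 0.05 is 2.011, giving power 0.901.
- n = 40, SD 4.8: 3 / (4.8 × 0.2236) = 2.795 on 78 df. The critical value at 0.05 is 1.991, giving power 0.788.

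Both match the protocol (about 90% and 79%).

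**Step 2: the floor under Hochberg.** If the other arm does not reach 0.05, an arm needs p ≤ 0.025.

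- n = 25: critical value 2.314, power 0.838.
- n = 40: critical value 2.285, power 0.694.

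Hochberg power must lie between these values and those in Step 1.

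**Step 3: Hochberg itself.** An arm succeeds if its p ≤ 0.025, or if both arms have p ≤ 0.05. This was simulated with pairwise t-tests sharing the placebo arm, 2,000,000 trials per case. The table gives power for an arm with the 3-point effect, by the true effect of the other drug.

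| Other drug's effect | 25 per arm, SD 3.2 | 40 per arm, SD 4.8 |
|---|---|---|
| Stated, single test | 0.901 | 0.788 |
| 3 points | 0.888 | 0.761 |
| 2.25 points | 0.867 | 0.732 |
| 1.5 points | 0.847 | 0.709 |
| 0 | 0.841 | 0.697 |

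The loss is 1.3 and 2.7 points if both drugs work (0.901 − 0.888; 0.788 − 0.761), and 6.0 and 9.1 points if one does (0.901 − 0.841; 0.788 − 0.697). The other drug need not be inert: at half the planned effect the result is within about 1 point of the zero-effect row.

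**Step 4: checks.** Pooling the variance over three arms gives 0.892 and 0.848 (25 per arm) and 0.764 and 0.703 (40 per arm) for both and one, all within 1 point of the table. The simulated familywise error under the global null is 0.048.

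**Step 5: what the baseline covariate could recover.** The documents give no correlation r between baseline and change, so r is an assumption here. Residual SD = SD × √(1 − r²).

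- 25 per arm: r = 0.20 gives 0.901 (both work). If one works, r of about 0.39 restores the stated figure; r = 0.40 gives 0.903.
- 40 per arm: r = 0.25 gives 0.789 (both work). If one works, r = 0.40 gives 0.780 and r = 0.45 gives 0.802, so about 0.42 restores 0.788.

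Equivalently, without covariate adjustment, 79% under Hochberg at 40 per arm holds up to an SD of 4.8 × √(1 − 0.25²) = 4.65 if both work, or 4.8 × √(1 − 0.42²) = 4.36 if one does, rather than 4.8.

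**The case against.** The strongest reply is that nothing is miscalculated. The protocol names the test and level for each figure, and it introduces Hochberg separately. That is true, and the point is about what the figures describe, not about an error in them.

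Second, the plan assumes that both drugs work: Protocol 8.1 posits 3 points for each arm, and SAP 7.11 assumes equal change in both for the blinded variance calculation. On that assumption the gap is about 1 point at 25 per arm, which is negligible, and about 3 points at 40 per arm. This stands. The 84% and 70% are sensitivity cases, though realistic ones for two unrelated mechanisms.

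Third, the replacement figures are not the power of the MMRM either. This also stands. The covariate could restore everything, and missing Week 12 data would work the other way. But the stated figures rest on the same t-test, so the comparison is like with like.

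Fourth, the chance that at least one arm succeeds when both drugs work is about 94% (25 per arm) and 85% (40 per arm), above the stated figures. That is correct, but the protocol attaches its figures to each arm.

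Fifth, SAP section 5, to which SAP 7.11 refers for sample size, was not in the text available for this review and may give a Hochberg figure. Protocol 8.1 and the synopsis would still lack one.

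**Conclusion.** The concern holds. The stated 90% and 79% are right for one unadjusted test but overstate each arm's power under the planned multiplicity rule: by 1 to 3 points if both drugs have the 3-point effect, and by 6 to 9 points if only one does. The practical weight falls on the 79% at the 120-subject maximum, which becomes 76% or 70%. These figures assume t-tests, the planned SDs, complete Week 12 data and no baseline adjustment. The net gap for the MMRM cannot be determined from the documents. Nothing here affects the validity of the primary analysis or its error control.

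**What to change.** In Protocol 8.1 and the synopsis, label the 90% and 79% as single-test power without multiplicity adjustment, and add text such as:

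> Under the Hochberg procedure, per-arm power is about 89% (both drugs with the 3-point effect) or 84% (only one) with 25 per arm and SD 3.2, and about 76% or 70% with 40 per arm and SD 4.8. These figures are t-test based, with no missing data and no baseline adjustment; the baseline covariate in the MMRM may recover some or all of the loss.

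The cost is wording only, plus less favourable printed figures. Enrolment, significance level and analysis stay as they are.
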